## 5. Study Design

### 5.1. Summary of Study Design

[figure not shown]
Study I4V-MC-JAIY (JAIY) is a Phase 3, multicenter, randomized, double-blind, placebo-controlled, parallel-group, outpatient study evaluating the efficacy and safety of baricitinib 2 mg QD and 4 mg QD, in combination with TCS, as compared to placebo in combination with TCS, in adult patients with moderate to severe AD. The study is divided into 3 periods, a 5-week Screening period, a 16-week Double-Blinded Treatment period, and a 4-week Post-Treatment Follow-Up period. For those patients who complete the 16-week treatment period, there is an option to participate in the long-term extension study I4V-MC-JAHN (JAHN).

Approximately 300 patients  $\geq 18$  years of age who have responded inadequately to topical therapy will be randomized at a 1:1:1 ratio to receive placebo QD, baricitinib 2 mg QD, or baricitinib 4 mg QD in combination with TCS (100 patients in each treatment group). Patients will be stratified at randomization according to disease severity (Investigator's Global Assessment [IGA] 3 vs. 4) and geographic region.

Study JAIY will consist of 3 periods:

- Period 1: Screening period is between 8 and 35 days prior to Week 0 (Visit 2)
- Period 2: Double-Blind, Placebo-Controlled Treatment period from Week 0 (Visit 2) through Week 16 (Visit 8)
- Period 3: Post-Treatment Follow-Up period from last treatment visit at Week 16 (Visit 8) or Early Termination Visit (ETV) to approximately 28 days after the last dose of investigational product

Figure JAIY.5.1 illustrates the study design. The blinding procedure is described in the Protocol.

**Figure JAIY.5.1. Illustration of study design for Clinical Protocol I4V-MC-JAIY.**

Abbreviations: AD = atopic dermatitis; eGFR = estimated glomerular filtration rate; PPD = purified protein derivative; QD = once daily; TCS = topical corticosteroids; V = visit; W = week.

- Applicable to patients taking topical treatments (excluding emollients) or systemic treatments for AD at the time of screening.
- For patients randomized to the 4-mg once daily dose who have renal impairment (defined as eGFR <60 mL/min/1.73 m^2), the baricitinib dose will be 2 mg once daily.
- Patients for whom PPD skin test for the evaluation of tuberculosis infection was performed at V1 must return and PPD test must be read 48 to 72 hours after Visit 1 (post-PPD).
- Occurs approximately 28 days after the last dose of investigational product. Not required for those patients entering the long-term extension study JAHN.

## 5.2. Method of Assignment to Treatment

Patients who meet all criteria for enrollment will be randomized in a 1:1:1 ratio (placebo; baricitinib 2 mg; baricitinib 4 mg) to double-blind treatment at Visit 2 (Week 0). Randomization will be stratified by geographic region (Europe [EU], Japan [JPN], rest-of-world [ROW]) and disease severity at baseline (IGA 3 vs. 4). Assignment to treatment groups will be determined by a computer-generated random sequence using an IWRS. The IWRS will be used to assign packages containing double-blind investigational product tablets to each patient according to the study schedule of activities. Site personnel will confirm that they have located the correct packages by entering a confirmation number found on the packages into the IWRS.

This study will be conducted internationally in multiple sites. [Table JAIY.5.1](#) describes how regions will be defined for stratification. Regions may be combined for statistical analyses in the

case when one of the region strata fails to meet the required minimum number of 30 patients. The 2 region strata with the least number of patients will then be pooled.

**Table JAIY.5.1. Geographic Regions for Stratification**

Region	Countries
Europe	Germany, Italy, Poland, Spain, Austria
Japan	Japan
Rest of World	Taiwan, Australia, Korea, Argentina

## 6. A Priori Statistical Methods

### 6.1. Determination of Sample Size

Study JAIY will aim to enroll approximately 300 patients  $\geq 18$  years of age. The proposed sample size will ensure a 89% power to detect an absolute difference of 20% between the baricitinib 4 mg and placebo treatment groups and the baricitinib 2 mg and placebo treatment groups, each using a 2-sided alpha of 0.025 and a Fisher's exact test, assuming a 10% placebo response rate for the primary endpoint. The assumptions are based on what was observed in the Phase 2 study (JAHG). The proposed end point of IGA 0 or 1 represents patients whose AD is clear or almost clear from a baseline of moderate or severe disease. The anticipated effect size represents 2 times more patients achieving this benefit compared to placebo, which, in discussion with therapeutic experts, is of a magnitude that is considered clinically relevant.

Sample size and power estimates were obtained from nQuery® Advisor 7.0.

### 6.2. General Considerations

This plan describes *a priori* statistical analyses for efficacy, health outcomes, and safety that will be performed.

Statistical analysis of this study will be the responsibility of Eli Lilly and Company (Lilly). The statistical analyses will be performed using SAS® Version 9.4 or higher.

Not all displays described in this SAP will necessarily be included in the clinical study report (CSR). Not all displays will necessarily be created as a "static" display. Some may be incorporated into interactive display tools instead of or in addition to a static display. Any display described in this SAP and not included in the CSR will be available upon request.

Statistical tests of treatment effects and confidence intervals (CIs) will be performed at a 2-sided significance level of 0.05, unless otherwise stated (e.g., graphical multiple testing strategy in Section 6.6).

Data collected at ETVs will be mapped to the closest scheduled visit number for that patient if it falls within the visit window as discussed in Section 6.2.2. For by-visit summaries, only visits in which a measure was scheduled to be collected will be summarized. Any unscheduled visit data will be included at the patient-level listings. However, the data will still be used in other analyses, including shift analyses for safety analytes, change from baseline using modified last observation carried forward (mLOCF) for efficacy analyses, and other categorical analyses including safety.

#### 6.2.1. Analysis Populations

**Intent-to-treat (ITT) population:** The ITT population analysis set is defined as all randomized patients.

**Per-protocol Set (PPS):** PP subset of the ITT analysis set will include those patients who do not have any significant or important protocol violations. Qualifications for and identification of

significant or important protocol violations will be determined while the study remains blinded, prior to database lock.

**Follow-up population:** The follow-up population is defined as patients who entered the follow-up period.

Unless otherwise specified, the efficacy and health outcome analyses will be conducted on the ITT population (Gillings and Koch 1991), which seeks to preserve the benefits of randomization and avoid selection bias. Patients will be analyzed according to the treatment to which they were randomized. In addition, the analyses of primary and key secondary endpoints will be repeated using the PPS population.

**Safety population:** The safety population is defined as all randomized patients who receive at least 1 dose of investigational product and who did not discontinue from the study for the reason 'Lost to Follow-up' at the first postbaseline visit.

Safety analyses will be performed using the safety population. Patients will be analyzed according to the treatment regimen to which they were assigned. Analyses of the safety endpoints, many of which are incidence based, will include all patients in the safety population, unless specifically stated otherwise.

In the rare situation where a patient is Lost to Follow-up at the first postbaseline visit, but some safety data exists (e.g., unscheduled laboratory assessments) after first dose of study drug, a listing of the data or a patient profile may be provided, when requested.

### **6.2.2. Definition of Baseline and Postbaseline Measures**

The baseline value for efficacy and health outcomes variables measured at scheduled visits is defined as the last non-missing measurement on or prior to the date of first study drug administration (expected at Week 0, Visit 2).

The baseline value for the daily diary assessments (Itch NRS, ADSS, Skin Pain NRS, PGI-S-AD) is the mean of the non-missing assessments in the 7 days prior to the date of first study drug administration (expected at Week 0, Visit 2).

If there are less than 4 non-missing assessments in the baseline diary window, the interval lower bound can be extended up to 7 additional days, one day at a time, to obtain the most recent 4 non-missing values. If there are not at least 4 non-missing assessments in the baseline period, the baseline mean is missing.

Baseline for the safety analyses is defined as the last non-missing scheduled (planned) measurement on or prior to the date of first study drug administration for continuous measures by-visit analyses and all non-missing measurements on or prior to the date of first study drug administration for all other analyses.

Postbaseline measurements are collected after study drug administration through Week 16 (Visit 8) or early discontinuation visit. Efficacy data collected at scheduled visits (e.g., eCOA, ClinRO) will be used in all analyses unless it is missing. If an assessment is missing at a scheduled visit, an unscheduled post-baseline assessment can be used provided it falls within the

window interval as follows: a  $\pm 2$  day window is used for Visit 3 (Week 1), Visit 4 (Week 2), and Visit 5 (Week 4); and a  $\pm 4$  day window is used to Visit 6 (Week 8), Visit 7 (Week 12), and Visit 8 (Week 16). If there is more than 1 unscheduled visit within the defined visit window and no scheduled visit assessment is available, the unscheduled visit closest to the scheduled visit date will be used. If two unscheduled visits of equal distance are available, then the latter of the two will be used.

Postbaseline daily diary endpoints will be the mean of weekly visit windows (diary windows) anchored on day of first dose (Day 1) for Weeks 1 through 14 as follows: Week 1 (Days 1 through 7), Week 2 (Days 8 through 14), Week 3 (Days 15 through 21), ..., Week 14 (Days 92 through 98).

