5.1.2. Period 2: Double-Blind, Placebo-Controlled Treatment

At Visit 2 (Week 0, baseline), study eligibility for each patient will be reviewed, based on all inclusion and exclusion criteria (Section 6), and laboratory test results. Patients who meet all criteria will proceed to randomization and begin the 16-week double-blind, placebo-controlled treatment period.

At Visit 2, after laboratory samples are collected and all assessments are completed, patients will take the first dose of investigational product at the clinic.

Patient will be randomized at a 1:1:1 ratio into 1 of the 3 treatment groups (placebo QD, baricitinib 2-mg QD, or baricitinib 4-mg QD). Investigational product will be administered daily for 16 weeks (treatment period Visits 2 through 8; Section 7). All patients will be required to use emollients daily. Daily diaries will continue to be utilized throughout the treatment period. Download of this data will be required at study visits. TCS will be dispensed at V2 and used on affected areas as described in section 7.7.2. Topical calcineurin inhibitors (TCNIs) is also allowed, but TCNI use should be limited to problem areas (e.g. face and skin folds). The use of higher potency TCS and systemic therapies for the treatment of AD are not allowed, except as part of rescue therapy for patients not responding to treatment. Details of background topical therapy, as well as rescue therapy and rescue criteria are included in Section 7.7. Assessments of disease severity will be performed by the investigator at all study visits including unscheduled and early termination visits (ETVs).

The primary efficacy endpoint and final visit in the treatment period will be at Week 16 (Visit 8). Patients who complete through the Week 16 study visit may be eligible for inclusion in the long-term extension study JAHN (up to 2 additional years of treatment).

If a patient discontinues investigational product for any reason, the patient should remain in the study through Week 16 (Visit 8). If the patient refuses and wishes to withdraw consent, an ETV should be performed as soon as logistically possible.

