9.1.3.3. Atopic Dermatitis Sleep Scale

The Atopic Dermatitis Sleep Scale (ADSS) is a 3-item, patient-administered questionnaire developed to assess the impact of itch on sleep including difficulty falling asleep, frequency of waking, and difficulty getting back to sleep last night. Patient’s rate their difficulty falling asleep and difficulty getting back to sleep, items 1 and 3, respectively, using a 5-point Likert-type scale with response options ranging from 0 “not at all” to 4 “very difficult.” Patients report their frequency of waking last night, item 2, by selecting the number of times they woke up each night, ranging from 0 to 29 times. The ADSS is designed to be completed each day with respondents thinking about sleep “last night.” Each item is scored individually.

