### **Handling of Duplicate Diary Records**

If there is more than one diary record on a particular date, the first record on that particular date will be used in the analysis.

Note, as some analyses require use of the primary censoring rule, assessments collected on the day of rescue or afterwards will be excluded from the weekly visit interval calculation when implementing the rule for daily diary. If, after exclusion of these records, there are less than 4 non-missing assessments, the weekly interval which implements the primary censoring rule will be missing. The post-study follow-up weekly score for daily diaries will be calculated as the mean of the 7 days prior to the follow-up visit which occur after last dose of study treatment.

Postbaseline measures for the safety analyses are defined as the non-missing scheduled (planned) measurements after the date of first study drug administration for continuous measures by-visit analyses and all non-missing measurements after the date of first study drug administration for all other analyses.

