Atopic Dermatitis Sleep Scale (ADSS)	The Atopic Dermatitis Sleep Scale (ADSS) is a 3-item, patient-administered questionnaire developed to assess the impact of itch on sleep including difficulty falling asleep, frequency of waking, and difficulty getting back to sleep last night. Patient's rate their difficulty falling asleep and difficulty getting back to sleep, items 1 and 3, respectively, using a 5-point Likert-type scale with response options ranging from 0 "not at all" to 4 "very difficult." Patients report their frequency of waking last night, item 2, by selecting the number of times they woke up each night, ranging from 0 to 29 times. The ADSS is designed to be completed each day with respondents thinking about sleep "last night." Each item is scored individually.	
 
▪ Item 1 score of ADSS
 
▪ Item 2 score of ADSS
 
▪ Item 3 score of ADSS
 
	Single items: Item 1, range 0 to 4; Item 2, range 0 to 29; Item 3, range 0 to 4. Refer to Section 6.2.2 on how to derive the visit score.	Refer to Section 6.2.2 on how to derive the weekly visit score.
		
 
▪ Change from baseline in score of Item 1 of ADSS
 
▪ Change from baseline in score of Item 2 of ADSS
 
▪ Change from baseline in score of Item 3 of ADSS
 
	Change from baseline: observed ADSS item score – baseline ADSS item score	Missing if baseline or observed value is missing.

Measure	Description	Variable	Derivation / Comment	Imputation Approach if Missing Components
Patient- Oriented Eczema Measure (POEM)	The POEM is a simple, 7-item, patient-administered scale that assesses disease severity in children and adults. Patients respond to questions about the frequency of 7 symptoms (itching, sleep disturbance, bleeding, weeping/oozing, cracking, flaking, and dryness/roughness) over the last week. Response categories include “No days,” “1-2 days,” “3-4 days,” “5-6 days,” and “Every day” with corresponding scores of 0, 1, 2, 3, and 4, respectively. Scores range from 0-28 with higher total scores indicating greater disease severity (Charman et al. 2004).	POEM score	POEM total score: sum of questions 1 to 7, Range 0 to 28.	If a single question is left unanswered, then that question is scored as 0. If more than one question is unanswered, then the tool is not scored. If more than one response is selected, then the response with the highest score is used.

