	Proportion of patients achieving a 4- point improvement in Skin Pain NRS in subgroup of patients with baseline Skin Pain NRS $\geq 4$	Logistic regression using NRI	ITT	Bari 4 mg or Bari 2 mg vs PBO; Week 1,..., 16	Other Secondary Analysis
Atopic Dermatitis Sleep Scale (ADSS)	
 
ADSS item scores
 
Change from baseline in ADSS item scores
 
	MMRM	ITT	Bari 4 mg or Bari 2 mg vs PBO; Week 1,..., 16	Key Secondary Analysis at Week 1 and 16
			PPS	Bari 4 mg or Bari 2 mg vs PBO; Week 16	Sensitivity analysis
		ANCOVA using mLOCF	ITT	Bari 4 mg or Bari 2 mg vs PBO; Week 1,..., 16	Sensitivity Analysis
		pMI	ITT	Bari 4 mg or Bari 2 mg vs PBO; Week 16	Sensitivity analysis
Patient-Oriented Eczema Measure (POEM)	
 
POEM score
 
Change from baseline in POEM score
 
	MMRM	ITT	Bari 4 mg or Bari 2 mg vs PBO; at each post-baseline visit	Secondary Analysis
			ANCOVA using mLOCF	ITT	Bari 4 mg or Bari 2 mg vs PBO; Week 16
	Proportion of patients achieving a 4- point improvement in subgroup of patients with baseline POEM $\geq 4$	Logistic regression using NRI	ITT	Bari 4 mg or Bari 2 mg vs PBO; at each post-baseline visit	Secondary Analysis
Patient Global Impression of Severity–Atopic Dermatitis (PGI-S- AD)	
 
PGI-S-AD score
 
Change from baseline in PGI-S-AD score
 
	MMRM	ITT	Bari 4 mg or Bari 2 mg vs PBO; at each post-baseline visit	Secondary Analysis
			ANCOVA using mLOCF	ITT	Bari 4 mg or Bari 2 mg vs PBO; Week 16

Measure	Variable	Analysis Method (Section 6.2.3)	Population (Section 6.2.1)	Comparison/Time Point	Analysis Type
Hospital Anxiety Depression Scale (HADS)	
 
HADS domain scores
 
Change from baseline in HADS domain
 
	MMRM	ITT	Bari 4 mg or Bari 2 mg vs PBO; Week 2, 4, 8, 16	Secondary Analysis
		ANCOVA using mLOCF	ITT	Bari 4 mg or Bari 2 mg vs PBO; Week 16	Sensitivity Analysis
Dermatology Life Quality Index (DLQI)	
 
DLQI total score
 
Change from baseline in DLQI
 
Observed and change from baseline in domain scores 
 
-Symptoms and feelings
 
-Daily activities
 
-Leisure
 
-Work and school
 
-Personal relationships
 
-Treatment
 
 
 
	MMRM	ITT	Bari 4 mg or Bari 2 mg vs PBO; Week 16	Secondary Analysis

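### The Week 1 diary window counts Day 1, but a Day 1 ADSS entry reports the night before the first dose, so the Week 1 ADSS Item 2 comparison is diluted toward the null

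*SAP*

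**What the plan says.** - **First dose.** Under Protocol 5.1.2, at Visit 2 "after laboratory samples are collected and all assessments are completed, patients will take the first dose of investigational product at the clinic". That date is Day 1.
- **Recall period.** Protocol 9.1.3.3 says of ADSS Item 2: "Patients report their frequency of waking last night, item 2, by selecting the number of times they woke up each night". SAP Table JAIY.6.6 confirms daily completion about the previous night: "The ADSS is designed to be completed each day with respondents thinking about sleep" (the sentence goes on to name last night).
- **Baseline.** SAP 6.2.2 takes the mean over the seven days before the first-dose date, so Day 1 is not in baseline.
- **Week 1.** The same section defines post-baseline diary windows "anchored on day of first dose (Day 1) for Weeks 1 through 14 as follows: Week 1 (Days 1 through 7". One calendar rule serves all four daily diary measures, with no offset for ADSS.
- **Same-day records.** Where one date has two records, "the first record on that particular date will be used in the analysis".
- **Status.** SAP 6.6 lists change in ADSS Item 2 at Week 1 among the key secondary null hypotheses for 4 mg and for 2 mg. Table JAIY.6.7 labels the ADSS MMRM "Key Secondary Analysis at Week 1 and 16".

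**The concern.** A diary entry belongs to the treatment period only if the time it reports on came after dosing. On Day 1 the ADSS looks back to a night that ended before the clinic visit, whatever hour the entry is made. Under randomisation the expected difference between arms for that night is zero, so averaging it with treated nights shrinks the Week 1 contrast.

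At stake are the Week 1 estimate and confidence interval for ADSS Item 2, and the chance of rejecting two hypotheses in the controlled family. No planned analysis would reveal the problem: the MMRM under both censoring rules and the mLOCF ANCOVA (Tables JAIY.6.1 and JAIY.6.7) all use the same window, and pMI for ADSS is set at Week 16.

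**Working it through.** **The plan's own figure.** The documents give no effect, SD or power for ADSS Item 2. The only power statement is for the primary endpoint: 89%, from 10% versus 30%, 100 per arm, two-sided alpha 0.025, Fisher exact test. Exact enumeration gives 89.1%, so it reproduces, but it says nothing about this endpoint.

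**Step 1: dilution for one patient.** Suppose a weekly mean uses k entries, one of them Day 1. The expected difference between arms is zero on Day 1 and has mean D over the other k − 1 nights. The expected difference in the weekly mean is D(k − 1)/k:

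- k = 7: 6/7 = 0.857
- k = 6: 5/6 = 0.833
- k = 5: 4/5 = 0.800
- k = 4: 3/4 = 0.750
- Day 1 entry absent: 1

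With complete diaries, 6/7 holds relative to the Days 2–7 mean whatever the shape of onset. As a check, a simulation with a true post-dose difference of 0.50 gave 0.427 on Days 1–7 and 0.498 on Days 2–7, a ratio of 0.858.

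**Step 2: incomplete diaries (completion rates assumed, at least four entries required).** If Day 1 is completed as often as any other day, its expected share of the kept entries is 1/7 by symmetry, so the factor stays 6/7. If Day 1 is always present and B of the other six days are present, the factor is 1 − E[1/(1 + B) | B ≥ 3]. At 90% completion:

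1 − (0.5314/7 + 0.3543/6 + 0.0984/5 + 0.0146/4)/0.9987 = 1 − 0.1585 = 0.84

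| Day 1 present | Other days present | Factor |
|---|---|---|
| 100% | 100% | 0.86 |
| same as other days | 90%, 80% or 70% | 0.86 |
| 100% | 90% / 80% / 70% | 0.84 / 0.82 / 0.81 |
| 50% | 100% / 90% / 80% | 0.93 / 0.92 / 0.91 |
| 0% | 90% | 1.00 |

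**Step 3: type I error.** With no treatment effect, rejection at nominal 0.05 was 5.4% in 4,000 simulated trials (Monte Carlo SE about 0.35 points), which is compatible with no inflation.

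**Step 4: illustrative power, complete diaries.** Assumptions: alpha 0.05, a single-visit ANCOVA on a seven-day baseline mean, daily correlation 0.4–0.8, and 80% power on Days 2–7. Power on Days 1–7 is Φ[(r/s)(1.960 + 0.842) − 1.960], where r = 6/7 and s is the residual SD of the Days 1–7 mean relative to Days 2–7. If only day-to-day noise matters, s is 0.957–0.960. With s = 0.960, r/s = 0.893, and Φ(0.893 × 2.802 − 1.960) = Φ(0.54), about 71%. Between-patient variation in response, tau (in daily SDs), softens the loss:

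| tau | Power on Days 1–7 |
|---|---|
| 0 | 71% |
| 0.5 | 76–78% |
| 1 | 79% |
| 1.5 | 79–80% |

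**Step 5: cost of dropping Day 1.** The binomial probability of fewer than four entries rises from 0.3% (seven days) to 1.6% (six days) at 90% completion, and from 3.3% to 9.9% at 80%. Net power was then simulated with those patients counted as lost at Week 1 (100 per arm, correlation 0.6, alpha 0.05, effect set to give 80% on complete Days 2–7):

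| Completion | tau | Days 1–7 | Days 2–7 | Change (points) |
|---|---|---|---|---|
| 90% | 0 | 67.7% | 76.8% | +9 |
| 90% | 0.5 | 75.5% | 78.4% | +3 |
| 90% | 1.5 | 79.1% | 79.2% | 0 |
| 80% | 0 | 63.6% | 70.8% | +7 |
| 80% | 0.5 | 73.0% | 73.9% | +1 |
| 80% | 1.5 | 77.5% | 75.5% | −2 |

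**The case against.** **The general definition may already remove Day 1.** SAP 6.2.2 states: "Postbaseline measurements are collected after study drug administration through Week 16 (Visit 8) or early discontinuation visit". The Schedule of Activities lists ADSS at Visit 2, and dosing follows the Visit 2 assessments, so an entry made before the dose could be read as not post-baseline and dropped. This does not settle the matter. The window names Day 1 explicitly, and an entry made after the dose satisfies the sentence while still reporting the pre-dose night. What stands is that the dilution depends on a Day 1 entry existing and being kept. The documents do not state the hour of diary completion.

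**The bias is conservative and local.** This stands. The Week 16 ADSS comparison, the Day 2 itch comparison and the primary endpoint do not use this window. The testing graph is not shown, so neither the local alpha nor any alpha passed onward can be assessed.

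**The power case is weak.** This stands in part. The fall to 71% needs zero between-patient variation in response, the calculation is not the planned MMRM, and the net change from the fix runs from +9 to −2 points. The argument rests on a correctly defined estimate.

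**The per-protocol analysis may cover Week 1.** SAP 6.2.1 says key secondary analyses are repeated in that set, whereas Table JAIY.6.7 lists ADSS there at Week 16 only. A Week 1 run would use the same window, so it would not expose the dilution.

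**A Days 2–7 sensitivity analysis would be enough.** It would show the dilution but leave the multiplicity-controlled test on a mean that contains an untreated night.

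**Conclusion.** The concern holds. The SAP scores a pre-treatment night as post-baseline in a key secondary endpoint tested for both doses. With complete diaries, or with Day 1 completed as often as other days, the Week 1 difference is 6/7 of the Days 2–7 difference, about 14% too small. The factor is 0.81–0.84 if Day 1 is better completed than other days, 0.91–0.93 if half of patients have a Day 1 entry, and 1 for patients with none.

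The dilution factor rests on the recall period, the dose timing and randomisation, plus assumed completion rates where diaries are incomplete. The power figures rest on assumed effect, variance, alpha and completion, and are illustrative only. Because the error is conservative and confined to one time point, the change should be made but does not threaten the trial's main conclusions.

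**What to change.** Before unblinding, add one sentence to SAP 6.2.2: for the ADSS items, the Week 1 window is Days 2 through 7, with the same minimum of four non-missing entries. Report the Days 1–7 ADSS mean as a sensitivity analysis. Leave the other ADSS windows as written; a Days 2–8 window would take a day that belongs to Week 2.

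Leave the Itch NRS, Skin Pain NRS and PGI-S-AD windows, and the itch-free and pain-free day counts, unchanged. Their recall is 24 hours, and the pre-dose share of a Day 1 entry cannot be determined from the documents. A Days 2–7 sensitivity analysis for Week 1 itch is optional.

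The cost is one sentence and one date filter, with no new data. The SAP already filters diary entries by date ("assessments collected on the day of rescue or afterwards will be excluded from the weekly visit interval calculation"), and its revision history shows that weekly itch derivations in this section were revised in Version 2, which was approved before unblinding. The downsides are about 4% more noise-driven SD (1/0.96 = 1.04) and more missing Week 1 ADSS means, which the MMRM handles without setting them to nonresponse. The certain gain is an undiluted estimate; a power gain depends on diary completion and response variation.
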